9.5.2.3 Derivation of secondary [REDACTED] variables

- $OGIS = p_4 [(p_1 D_0 - V(G(120) - G(90))/30)/G(90) + p_3/G(0)] / [I(90) - I(0) + p_2]$, where D_0 (g/m^2) is the glucose dose included in the standard meal administered to patients who participate in the standard meal-test ($D_0 = 73.2 g/m^2$ for the standard meal as planned in [Section 6.4.3](#)), $V = 10$ (ml/m^2) is the assumed glucose distribution volume, $G(0)$, $G(90)$ and $G(120)$ are glucose concentration values at oGTT timepoints 0, 90 and 120 min, $I(0)$ and $I(90)$ are insulin concentration values at timepoints 0 and 90 min, $p_1 = 6.5$, $p_2 = 1951$, $p_3 = 4514$ and $p_4 = 792$ are constants ([Mari, et al 2001](#)).

AUC of ISR/G is defined as ISR relative to glucose 0-2h ($pmol/min/m^2/mM$) = AUC_{0-2hr} of ISR/ AUC_{0-2hr} of glucose.

Calculation of ISR

Separately for each patient and each meal challenge, deconvolution is applied to estimating insulin secretion to assess β -cell function. C-peptide, which is co-secreted with insulin in an equimolar ratio, is preferred to insulin as a basis for estimating insulin secretion. Mathematically, we need to solve for the insulin secretion rate r given the impulse response h , and plasma C-peptide c , where

[REDACTED]

$$c(t) = \int_{-\infty}^t h(t-s)r(s)ds.$$

The impulse response is the PK model for an intravenously administered unit bolus dose of C-peptide when the endogenous C-peptide production has been suppressed, i.e.

$$h(t-s) = (1/V)[fe^{-\alpha(t-s)} + (1-f)e^{-\beta(t-s)}],$$

where V , f , α , and β are a subject's parameters, which are generally unknown. However, from clinical studies these parameters have been estimated, and are related to a subject's disease status, body surface area, age, and gender. Thus, h becomes known.

Insulin secretion rates are modeled by a piecewise continuous linear function with knots at the actual sampling time. Changes in slopes are penalised through a single regularisation parameter that is determined by a root finding method to produce similar residual standard deviation for fitted C-peptide concentrations as would be expected from assay error standard deviations given in the kit instructions.

The IMMULITE 2000 C-peptide kit instructions were used to model intra-assay SD as a function of the true C-peptide concentration $C1$ expressed in conventional units of ng/mL by simple linear regression as:

$$SD = 0.04056C1 + 0.06311\text{ng/mL}.$$

With concentration of C-peptide expressed alternatively in SI units, i.e., $C2$ expressed in nM (1ng/mL C-peptide = 0.331nM C-peptide) the equations for SD becomes:

$$SD = 0.04056 C2 + 0.331 \times 0.06311\text{nM}.$$

The following ln-transformation with a shift parameter of observed and fitted C-peptide values is used to stabilize the variance in performing the deconvolution:

[figure not shown]
$$\ln(C1 + 0.06311/0.04056) \text{ or } \ln(C2 + 0.331 \times 0.06311/0.04056).$$

Nonlinear least squares with ISR constrained non-negative using PROC IML function NLPLM in SAS[®] is used to solve for ISR at the sampling time points using actual sampling times. The bisection method is used to iteratively determine the regularisation parameter such that the sum of squares of the observed C-peptide minus the fitted C-peptide expressed in either units equals $0.040562n$ where n is the number of non-missing C-peptide concentrations in the meal challenge.

Calculation of AUC

For the patients participating in the meal-test, glucose, insulin and C-peptide are also to be measured at the following 7 time-points (minutes in relation to the meal time): -20min, 0min (immediately prior to meal ingestion), 15min, 30min, 60min, 90min, 120min. Let L_1, L_2, \dots, L_7 denote the lab measurements at these 7 time-points (i.e., L_1 is the value measured at 20min pre-meal, L_2 is the value measured at 0min pre-meal, ..., L_7 is the value which should be measured about 2h after the meal) and T_1, T_2, \dots, T_7 be the corresponding times (actual times in units of h), the AUC_{0-2hr} is calculated (using the trapezoidal rule) as:

$$AUC_{0-2h} =$$

$$[(L_2 + L_3) \times (T_3 - T_2) + (L_3 + L_4) \times (T_4 - T_3) + (L_4 + L_5) \times (T_5 - T_4) + (L_5 + L_6) \times (T_6 - T_5) + (L_6 + L_7) \times (T_7 - T_6)] / 2.$$

9.5.3 Safety variables

[figure not shown]
The safety and tolerability of vildagliptin 50mg bid as add-on to metformin over 5-years of treatment will be compared to placebo as add-on to metformin based on data collected during the randomised treatment period in SAF set.

The assessment of safety will be based mainly on the frequency of treatment emergent AEs (including overall AEs), SAEs, death, AEs leading to study discontinuation or study drug interruption & pre-specified AE risks on the number of post BL laboratory values that fall outside of pre-determined ranges and on the frequency and severity of hypoglycemic events during the randomised treatment period. Summaries for safety assessment will be presented for the SAF set. Unless specified otherwise, comparison will be made to BL, which will be the measurement taken at Visit 3, or the sample obtained at an earlier visit (scheduled or unscheduled) which was closest to Day 1 if Day 1 measurement is missing.

AEs will be summarised by presenting, for each treatment group (vildagliptin 50mg bid + metformin, placebo + metformin), the number and percentage of patients having any AE, having an AE in each primary SOC and having each individual AE. Any other information collected (e.g. severity or relatedness to study medication) will be presented as appropriate.

[figure not shown]
Laboratory data will be summarised by presenting summary statistics of raw data and change from BL values (means, medians, standard deviations, ranges) and by presenting the number and percentage of patients having notable lab values or having endpoint change from BL meeting pre-specified percent change criteria. The identification of notable values will be based on the pre-specified criteria provided in the investigator binder (will also be included in the analysis plan). The predefined categories of liver enzyme (ALT/AST) and CPK elevations and persistent elevations will be summarised by treatment.

Hypoglycemia events will be included in all AE summaries. In addition, events will be characterised by event profile, such as ability to self-treat, self monitoring of plasma glucose level, precipitating event, time from last meal, time from last dose, and time of the day.

[figure not shown]
Data from other tests (e.g. vital signs including [redacted], ECGs) will be summarised as appropriate, incidences of notable values will be presented in the tables and notable values will be flagged in the listings.

All above safety analyses will be performed in the SAF on all available data collected during the entire study. In addition, key safety analyses will be performed on data obtained during Period 1 only.

9.5.4 Resource utilisation

Not applicable.

9.5.6 PK

Not applicable.

9.5.7 Pharmacogenetics/pharmacogenomics

Not applicable.

9.5.9 PK/pharmacodynamics

Not applicable.

9.6 Sample size calculation

A total sample size of 1000 randomised patients per treatment arm (in 1:1 allocation ratio to vildagliptin + metformin and metformin monotherapy) is planned.

Power calculation for the time-to-treatment failure variable

The sample size calculation assumes that all randomised patients are to be followed up for 5 years unless patients dropped out from the study for various reasons (lack of efficacy, AEs,

abnormal labs, lost to follow-up etc.), and that the yearly dropout rate is 11% (estimate based on ADOPT data (Kahn S et al, 2006)).

The existing vildagliptin study data suggest that approximately 10% of vildagliptin patients will have an HbA1c >7.0% after the first 3 months of the study (initial response phase), since those patients who are randomised with an HbA1c measurement above the failure threshold (7.0%) may never have an HbA1c measurement below the required threshold during the study and will therefore be counted as failures during the first 13 weeks. A similar proportion is assumed for the comparator arm. Hence it is expected that the difference in failure rate is likely to be small early in the study, but will diverge as the study progresses. The power calculations have been adjusted to take this assumption into account using statistical simulations.

The simulations showed that assuming an annual initial treatment failure rate of 7.1% in the metformin monotherapy arm (estimated based on ADOPT data), incorporating a 10% initial failure rate after 13 weeks in each treatment arm (due to some patients with BL HbA1c $\geq 7.0\%$), 1000 patients per treatment arm would be sufficient to detect a hazard-ratio of 0.75 between vildagliptin + metformin and metformin alone (corresponding to a risk reduction rate of 25% in vildagliptin + metformin group *versus* metformin alone) with approximate 66% power and a 1-sided significance level of 0.025 (corresponding to a 2-sided test at 0.05).

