9.4.2 Statistical model, hypothesis, and method of analysis

Time to initial treatment failure

The primary statistical hypothesis of time to confirmed initial treatment failure will be assessed by a 1-sided test of superiority of the combination treatment with vildagliptin + metformin versus metformin monotherapy with α -level of 0.025 of the hazard-ratio between the combination treatment vildagliptin + metformin and metformin monotherapy being equal or greater than 1 as the null hypothesis, versus the 1-sided alternative hypothesis that the hazard-ratio is less than 1:

$$H_{01}: \lambda_{\text{vildagliptin+metformin}} / \lambda_{\text{metformin}} \geq 1$$

versus

$$H_{a1}: \lambda_{\text{vildagliptin+metformin}} / \lambda_{\text{metformin}} < 1$$

where $\lambda_{\text{vildagliptin+metformin}}$ and $\lambda_{\text{metformin}}$ are the hazard-rates of the confirmed initial treatment failure for vildagliptin 50mg bid + metformin up to 1000mg bid and metformin up to 1000mg bid monotherapy respectively.

The time to confirmed failure will be derived as the time from randomization to the second of two consecutive visits at which HbA1c $\geq 7.0\%$ is measured, starting from Visit 4 (13 weeks after randomization).

The primary efficacy analysis will use a Cox proportional hazard regression model to assess the probability of confirmed initial treatment failure, with treatment as classification variable and BL HbA1c as a covariate. The hazard-ratio and associated 95% confidence interval as well as the p-value estimated from the above model will be presented by treatment.

The confirmed initial treatment failure rate over time by treatment will be summarised and plotted with associated 95% confidence intervals, using estimates from a Kaplan-Meier analysis.

The primary analysis for this primary efficacy variable will be performed using the FAS. It will be performed in the PP set as supportive analysis as well.

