2.7 Determination of sample size

A total sample size of 1000 randomized patients per treatment arm (in 1:1 allocation ratio to vildagliptin + metformin and metformin monotherapy) is planned.

The sample size calculation assumed that all randomized patients are to be followed up for 5 years unless patients dropped out from the study for various reasons (lack of efficacy, AEs, abnormal labs, lost to follow-up etc.). Including the updated information of the yearly dropout rate being approximately 4% (based on observed discontinuation rate for this study at the time of completion of the trial).

The existing vildagliptin study data suggest that approximately 10% of vildagliptin patients will have an HbA1c >7.0% after the first 3 months of the study (initial response phase), since those patients who are randomized with an HbA1c measurement above the failure threshold (7.0%) may never have an HbA1c measurement below the required threshold during the study and will therefore be counted as failures during the first 13 weeks. A similar proportion is assumed for the comparator arm. Hence it is expected that the difference in failure rate is likely to be small early in the study, but will diverge as the study progresses. The power calculations have been adjusted to take this assumption into account using statistical simulations.

The simulations showed that assuming an annual initial treatment failure rate of 7.1% in the metformin monotherapy arm (estimated based on ADOPT data), incorporating a 10% initial failure rate after 13 weeks in each treatment arm (due to some patients with baseline HbA1c $\geq 7.0\%$), 1000 patients per treatment arm would be sufficient to detect a hazard-ratio of 0.75 between vildagliptin + metformin and metformin alone (corresponding to a risk reduction rate of 25% in vildagliptin + metformin group versus metformin alone) with approximate 75% power and a 1-sided significance level of 0.025 (corresponding to a 2-sided test at 0.05).

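### The stated 66% and 75% power leave out the confirming visit that defines the primary event; the cost depends on what the 7.1% yearly rate means, which the plan does not say

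*Protocol*

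**What the plan says.** Protocol 9.6 plans 1000 patients per arm, 1:1. It assumes five years of follow-up, 11% yearly dropout, a 7.1% annual failure rate on metformin alone, and 10% early failures in each arm. Those early failures "will therefore be counted as failures during the first 13 weeks". The section says the sample size "would be sufficient to detect a hazard-ratio of 0.75" with "approximate 66% power and a 1-sided significance level of 0.025". SAP V3.0, 2.7, keeps the same text, replaces the dropout by about 4%, and gives "approximate 75% power and a 1-sided significance level of 0.025".

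The endpoint is defined elsewhere. Protocol 9.4.2 states: "The time to confirmed failure will be derived as the time from randomization to the second of two consecutive visits". Both values must be at least 7.0%, and the first counts from Visit 4 (Week 13). Protocol 3.2 and Tables 6-1 and 6-2 put visits 13 weeks apart, with the last at Week 260. Protocol 9.4.3 censors patients whose elevated value is not confirmed. The slope analysis in SAP 2.2.3.3 itself treats Week 26 as the time of the earliest failures.

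SAP 2.8 records that the event date was moved to the second measurement and that the power was updated for the single primary endpoint and the known retention. Protocol Amendment 4 clarified the same definition and edited 9.6. The Week 13 sentence remains in Protocol 9.6, in SAP V3.0 and in SAP Addendum 1.

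**The concern.** The power is quoted for the only primary endpoint, but the description behind it fits a different event: a failure counted when it first appears, as early as Week 13. Under the defined event, nothing counts before nominal Week 26. A first elevation at Week 260 can never be confirmed, and some patients leave between the first and second elevated visit. If the simulation used the event that 9.6 describes, the stated power is too high for the event that will be analysed. A non-significant result would then be read against too favourable a figure.

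**Working it through.** **Inputs.** From Protocol 9.6: 1000 per arm, HR 0.75, one-sided 0.025, 7.1% per year on metformin, 10% early failures per arm, 5 years, dropout 11%. From SAP V3.0, 2.7: dropout 4%. As yearly hazards:
- metformin: −ln(1 − 0.071) = 0.0736
- combination: 0.75 × 0.0736 = 0.0552
- dropout μ: −ln(0.89) = 0.1165, or −ln(0.96) = 0.0408

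**1. Reproduce the stated figures.** Expected events per arm of n patients: n·λ/(λ+μ)·[1 − exp(−5(λ+μ))].

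- Ignoring early failures (n = 1000), 11% dropout: 237.6 + 185.3 = 423 events, power Φ(0.2877·√(423/4) − 1.96) = 84%. At 4%: 280.4 + 219.3 = 500 events, 90%. Both are far above the stated values, so the stated values do include the early failures.
- With 10% of each arm failing at Week 13, the early events are 200·exp(−μ/4) = 194 (or 198) and carry no treatment effect. The other 90% give 381 (or 450). A dilution approximation is z = 0.2877 × informative events / (2√total events).
  - 11%: 0.2877 × 381/(2√575) = 2.28, power Φ(0.32) = 63%.
  - 4%: 0.2877 × 450/(2√648) = 2.54, power Φ(0.58) = 72%.
- A simulated log-rank test (30,000 trials per setting in the main runs) gives 64.5–65.6% and 73.7–74.2% across dropout conventions, with 67.4% if all 11% dropout falls at year end. The stated 66% and 75% are reproduced within 2 points.

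**2. Apply the 9.4.2 rule to the same inputs.** The first elevation is seen at the next 13-weekly visit. The event is dated one visit later and counts only if that visit takes place by Week 260 and before dropout.

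| Expected events, both arms | 11% dropout | 4% dropout |
|---|---|---|
| Counted as in 9.6 | 574.9 | 647.8 |
| Seen only at visits | 569.4 | 645.4 |
| First elevation at Week 260, cannot be confirmed | −11.8 | −17.2 |
| Dropout before the confirming visit: 1 − exp(−μ/4) = 2.87% or 1.02% of the rest | −16.0 | −6.4 |
| Confirmed events | 541.6 | 621.8 |

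The Week 260 row is 900·[exp(−4.75λ) − exp(−5λ)]·exp(−5μ), summed over arms: 6.5 + 5.3 and 9.4 + 7.7 (17.2 before rounding). Informative events become about 353 and 426. The approximation gives 0.2877 × 353/(2√541.6) = 2.18, power 59%, and 0.2877 × 426/(2√621.8) = 2.46, power 69%. The simulation gives 60.3–61.6% and 70.3–70.5% (year-end dropout: 63.6% and about 70%).

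Like for like, the simulated loss is 64.5 − 60.3 = 4.2 or 65.6 − 61.6 = 4.0 points at 11%, and 73.7 − 70.3 = 3.4 points at 4%.

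**3. Isolate the cause.** Moving only the 10% early failures from Week 13 to Week 26 gives 64.9% against 64.5%, and 73.8% against 73.7%. That step costs nothing. The loss comes from the second-visit requirement.

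**4. Vary the meaning of 7.1% per year.**

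| Reading | 11% dropout | 4% dropout |
|---|---|---|
| First elevations, each needing confirmation at the next visit | 60–62% | 70% |
| Confirmed failures, accruing only after Week 26 | about 57% | 67% |
| Confirmed failures, accruing from day 1, early events held to Week 26 | 63–66% | 74% |

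**The case against.** The strongest reply is that 7.1% is already a confirmed rate. Protocol 9.6 calls it an initial treatment failure rate, and 9.4.1 and SAP 2.8 use that term for the event defined by two values. On that reading the power hardly moves, and the stated figures survive apart from their wording. This stands as a possibility, and for that reason no single corrected figure can be given. It is not established. The plan says only that 7.1% was estimated from ADOPT, and the ADOPT metformin figures it quotes (Protocol 1.1: 21% at five years, 4.3 per 100 patient-years) concern a fasting glucose criterion.

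Second, patients who leave between visits are not all lost. Protocol Section 6 asks for the final-visit assessments at discontinuation, and SAP 1.3.2 assigns that visit to the nearest unallocated one. It might therefore confirm a failure, although 9.4.3 censors discontinuers. If all such visits confirm, events at 11% dropout are about 558 rather than 542, and power changes by less than 1 point. SAP 1.3.2 also allows nearly 28 days either side of a visit, so Week 26 is nominal.

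Third, the check uses an unadjusted log-rank test, whereas the planned Cox model adjusts for baseline HbA1c and, in the SAP, region. The effect of that adjustment on power was not examined.

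Fourth, the consequence is limited. The sample size is fixed, and the test, alpha, hazard ratio and confidence interval are untouched. The power was openly below 80%, and both figures are labelled approximate. All of this stands and limits the weight of the point.

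**Conclusion.** The mismatch is real. The sample-size text describes an event that the primary endpoint does not allow, and it was carried through revisions that changed or clarified the event date. The supportable size is a range: about 57–66% at 11% dropout and 67–74% at 4%, against the stated 66% and 75%. Where 7.1% is a first-elevation rate, the figures are about 60–62% and 70%, a like-for-like loss of about 3–4 points.

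The documents do not support three stronger inferences that a reader might draw:
- That the power simply is 61% and 70%. This holds only under one unstated reading of 7.1%.
- That the gap is 5 points. Setting 61% and 70% against the stated values adds 1–2 points of modelling difference to the real loss.
- That counting failures in the first 13 weeks causes the loss. Correcting that sentence alone changes no figure.

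The result assumes constant hazards after the early failures, a hazard ratio of 0.75 from randomisation (from Week 26 under the second reading) and a log-rank test. The simulation code is not in the documents.

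**What to change.** Rerun the simulation under the rule in Protocol 9.4.1 and 9.4.2: 13-weekly visits, the event at the second of two elevated values, none before Week 26, and no confirmation after Week 260. State whether 7.1% and 10% are first-elevation or confirmed rates and how they were obtained. State whether a discontinuation visit can serve as the confirming visit. Restate the resulting power, or its range, in Protocol 9.6 and SAP 2.7, and replace the Week 13 wording.

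At the same time, reconcile SAP Addendum 1, 2.7, which pairs 75% power with 11% dropout, with Protocol 9.6, which gives 66% for the same inputs. The runs above support about 65% for those inputs when failures are counted as in 9.6.

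The cost is one rerun of an existing simulation and a few sentences, with no change to design, data or analysis. The stated power may become slightly less favourable.

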9.7 Power for analysis of key secondary variables

Not applicable.

9.8 Interim analyses

An external and independent DMC to monitor patient safety data on a regular basis during the course of the study will be established. The DMC may request additional safety data review. Such safety analyses do not inflate the type I error for the primary efficacy hypothesis testing and thus require no multiplicity adjustments.

There is no efficacy interim analysis planned for the study.

10 Ethical considerations

10.1 Regulatory and ethical compliance

This clinical study was designed and shall be implemented and reported in accordance with the International Conference on Harmonisation of Technical Requirements for Registration of Pharmaceuticals for Human Use (ICH) Harmonised Tripartite Guidelines for GCP, with applicable local regulations (including European directive 2001/20/EC, US CFR Title 21, and Japanese ministry of health, labor, and welfare), and with the ethical principles laid down in the declaration of Helsinki.

10.2 Informed consent procedures

Eligible patients may only be included in the study after providing written (witnessed, where required by law or regulation), IRB/IEC-approved informed consent, or, if incapable of doing

so, after such consent has been provided by a legally acceptable representative of the patient. In cases where the patient's representative gives consent, the patient should be informed about the study to the extent possible given his/her understanding. If the patient is capable of doing so, he/she should indicate assent by personally signing and dating the written informed consent document or a separate assent form. Informed consent must be obtained before conducting any study-specific procedures (i.e. all of the procedures described in the protocol). The process of obtaining informed consent should be documented in the patient source documents.

Novartis will provide to investigators in a separate document a proposed informed consent form that complies with the ICH GCP guideline and regulatory requirements and is considered appropriate for this study. Any changes to the proposed consent form suggested by the investigator must be agreed to by Novartis before submission to the IRB/IEC, and a copy of the approved version must be provided to the Novartis monitor after IRB/IEC approval.

